
Primary
 
Safety: To determine the safety and reactogenicity of the hAd5-S-Fusion+N-ETSD vaccine at two dose levels for subcutaneous administration, and for sublingual and intranasal dosing.
 
Immunogenicity: To determine immunogenicity of hAd5-S-Fusion+N-ETSD as determined by changes in humoral response.
	
Safety:
 
 • Incidence of MAAEs and SAEs through 1 week post final vaccine administration • Incidence and severity of solicited local reactogenicity AEs through 1 week post final vaccine administration • Incidence and severity of solicited systemic reactogenicity AEs through 1 week post final vaccine administration • Incidence and severity of unsolicited AEs through 1 week post final vaccine administration • Incidence of MAAEs and SAEs through 30 days and 6 months post final vaccine administration • Incidence and severity of unsolicited AEs through 30 days and 6 months post final vaccine administration • Incidence of abnormal changes of laboratory safety examinations • Changes in vital signs 
Immunogenicity: Timing per Schedule of Events
 
 • GMFR in IgG titer to SARS-CoV-2 S, RBD and N. • GMT of S-specific, RBD-specific, and N-specific antibodies against 2019 novel coronavirus tested by ELISA in serum . • Percentage of participants who seroconverted (defined as 4-fold change in antibody titer relative to baseline) . • GMFR in neutralizing antibody .

	
 • GMT of neutralizing antibody . • Seroconversion rate of neutralizing antibody (defined as 4-fold change in antibody titer relative to baseline) .
Secondary	
Safety: 
 • Ascertainment of HIV infections in vaccine recipients through 12 months post final vaccine administration 	Safety: 
 • New HIV infections in vaccine recipients by either two locally approved rapid antibody tests or by ELISA, conducted per Schedule of Events through 12 months post final vaccine administration
Exploratory	

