Immunogenicity: To determine cellular and mucosal immunogenicity of hAd5-S-Fusion+N-ETSD. To assess for any induction or enhancement of Ad5 immune response by the Ad5 vector in hAd5-S-Fusion+N-ETSD.	Immunogenicity: Timing per Schedule of Events 
 • T cell activity against SARS-CoV-2 S, RBD and N protein • Mucosal Immunogenicity as assessed by GMT of IgA antibody levels to SARS CoV-2 S protein, RBD and N protein • T cell activity and IgG titres against Ad5, comparing baseline to day 29 and day 181 and 202(in cohorts 3, 4, 5, 6 and cohorts 1 and 2 respectively)

Study Design:

This is a phase 1b, open-label study in adult healthy participants. This clinical trial is designed to assess the safety, reactogenicity, and immunogenicity of the hAd5-S-Fusion+N-ETSD vaccine and select a dose for future studies. The hAd5-S-Fusion+N-ETSD vaccine is a hAd5 [E1-, E2b-, E3-] vector-based targeting vaccine encoding the SARS-CoV-2 S and N proteins. The hAd5-S-Fusion+N-ETSD vaccine is designed to induce both humoral and cellular responses even in individuals with pre-existing adenoviral immunity. Thus, the potential exists for the hAd5-S-Fusion+N-ETSD to induce SARS-CoV-2 immunity and prevent or lessen the health impact of COVID-19 infection in healthy participants. Up to 60 healthy participants will be divided into 6 cohorts:

Study Cohorts, Dosing Schedules, Mode of Administration and Dose of hAd5-S-Fusion+N-ETSD

Cohort	Number of participants	Dosing Schedule	Mode of Administration	Dose
1	10	Day 1	SC	5×10^{10} VP
		Day 22	SC	5×10^{10} VP
2	10	Day 1	SC	1×10^{11} VP*
		Day 22	SC	1×10^{11} VP*
3	10	Day 1	SC	1×10^{11} VP*
4	10	Day 1	SL	1×10^{11} VP
5	10	Day 1	SC	1×10^{11} VP*
			and SL	1×10^{11} VP
6	10	Day 1	IN	2×10^{10} VP into each nostril**

SC= subcutaneous; SL= sublingual; IN= intranasal; VP= viral particles; * In the event of safety concerns participants will be dosed at 5×10^{10} VP/dose; ** Total IN dose is given is 4×10^{10} VP as vaccine will be administered into both nostrils

Cohort 1-2 enrolled participants who were SARS-CoV-2 antibody serology negative. For cohorts 3-6, only participants who are SARS-CoV-2 antibody serology positive will be enrolled to evaluate boosting of pre-existing SARS-CoV-2 immune responses and compare the effect of route of administration on the efficacy (and magnitude thereof), reactogenicity and safety of the boosting effect.

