The Safety Review Committee (SRC), including at least one qualified infectious disease physician independent of the Sponsor and trial reviews safety data.

The SRC will first assess safety when all Cohort 1 participants have completed the toxicity assessment period (defined as 7 days after first vaccine dose, i.e. study day 8). In the absence of safety concerns, enrolment in Cohort 2 will be initiated. The SRC will similarly also assess safety when each of Cohort 2, 3, 4 and 5 participants have completed the toxicity assessment period (defined as 7 days after first vaccine dose, i.e. study day 8). In the absence of safety concerns, enrolment in Cohort 3, 4, 5 and 6 respectively will proceed. Cohorts 3 and 5 will be dosed at 1×10^{11} VP/dose for SC administrations. If safety concerns are identified at the higher dose of 1×10^{11} VP/dose, Cohort 3 and 5 participants will be dosed at 5×10^{10} VP/dose for SC administrations.

All participants will have follow up study visits for the collection of safety, reactogenicity, and/or immunogenicity data at 7 and 14 days after each vaccine dose, 30 days after the last dose, and at 90, 180 and 365 days following the last dose. Additional follow up for safety information will occur via telephone contact as noted in the Schedule of Events.

Safety will be assessed for all participants and will include monitoring of vital signs, and incidence and severity of AEs. Blood samples will be collected for haematology and chemistry analyses and urine samples will be collected for urinalysis. Toxicities will be graded using the Guidance for Industry: Toxicity Grading Scale for Healthy Adult and Adolescent Volunteers Enrolled in Preventive Vaccine Clinical Trials (2007). Solicited local and systemic AEs and unsolicited AEs will be collected using diary cards for 7 days following any dose of vaccine.

Solicited local AEs to be assessed include

Subcutaneous dosing includes injection site:

- Pain,
- Itching,
- Induration,
- Swelling,
- Erythema.

Sublingual dosing include:

- Oral burning,
- Oral swelling,
- Difficulty swallowing,
- Difficulty breathing.

Intranasal dosing include:

- Nasal congestion and coryza
- Epistaxis,
- Pain in the nose,

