
11. HIV positive or other acquired or hereditary immunodeficiency.
 
12. Serious cardiovascular diseases, such as arrhythmia, conduction block, previous myocardial infarction, uncontrolled severe hypertension
 
13. History of hereditary, idiopathic or acquired angioedema.
 
14. Urticaria 12 months prior to screening.
 
15. No spleen or functional asplenia.
 
16. Platelet disorder or other bleeding disorder that may cause injection contraindication.
 
17. Chronic use (more than 14 continuous days) of any medications that may be associated with impaired immune responsiveness including, but not limited to, systemic corticosteroids exceeding 10 mg/day of prednisone equivalent, allergy injections, immunoglobulin, interferon, or immunomodulators. The use of low dose topical, ophthalmic, inhaled and intranasal steroid preparations will be permitted.
 
18. Prior administration of blood products within 120 days before first study vaccination.
 
19. Prior administration of other research medicines or investigational product within 30 days before first study vaccination.
 
20. Prior administration of attenuated vaccine within 30 days before first study vaccination.
 
21. Prior administration of inactivated vaccine within 14 days before first study vaccination.
 
22. Prior administration of SARS-CoV-2 vaccine or likely to receive SARS-CoV-2 vaccination within the upcoming 28 days
 
23. Current treatment with investigational agents for prophylaxis of COVID-19.
 
24. Have a household contact that has been diagnosed with COVID-19 within 14 days before first study vaccination.
 
25. Current anti-tuberculosis prophylaxis or therapy.
 
26. Currently receiving treatment for cancer or history of cancer in the last five years (except basal cell carcinoma of the skin and cervical carcinoma in situ).
 
27. According to the judgement of the investigator any medical, psychiatric, psychological, social, occupational or other conditions that could affect the participants ability to sign informed consent, provide safety assessment data or comply with the requirements of the study protocol.
 
28. Assessed by the Investigator to be unable or unwilling to comply with the requirements of the protocol.
	
Duration of Treatment: Each participant will receive hAd5-S-Fusion+N-ETSD on Day 1. Cohorts 1 & 2 receive a second dose of hAd5-S-Fusion+N-ETSD at Day 22.

--	--

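### In the supplied synopsis and schedule, no Safety Review Committee assessment is tied to the Day 22 second dose in Cohorts 1 and 2, although second-dose data to Day 29 are part of the primary safety endpoints

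*Combined protocol and SAP*

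**What the plan says.** All references are to the combined protocol and SAP.

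- **SRC triggers (synopsis, Study Design).** The SRC first assesses safety once all Cohort 1 participants have finished the toxicity assessment period, "defined as 7 days after first vaccine dose, i.e. study day 8". It will "also assess safety when each of Cohort 2, 3, 4 and 5 participants have completed the toxicity assessment period", with the period defined in the same way. Each assessment governs whether the next cohort may enrol.
- **Second dose (synopsis, Duration of Treatment).** "Cohorts 1 & 2 receive a second dose of hAd5-S-Fusion+N-ETSD at Day 22". Cohorts 3 to 6 have one dosing day.
- **Data collection (synopsis, Study Design).** Solicited and unsolicited events "will be collected using diary cards for 7 days following any dose of vaccine". Table 9 schedules an in-person Day 29 visit with diary reconciliation and safety laboratory tests.
- **Primary endpoints (synopsis, Study Objectives and Endpoints).** These include "Incidence and severity of solicited systemic reactogenicity AEs through 1 week post final vaccine administration", with matching endpoints for local reactions, unsolicited events, MAAEs and SAEs.
- **Dose reduction.** The footnote to the cohort table begins "In the event of safety concerns participants will be dosed at" and names 5×10^10 VP. It marks both Cohort 2 doses and the subcutaneous doses in Cohorts 3 and 5. The SRC paragraph has a parallel rule for Cohorts 3 and 5, beginning "If safety concerns are identified at the higher dose of".
- **Status of the first two cohorts (synopsis, Study Design).** "Cohort 1-2 enrolled participants who were SARS-CoV-2 antibody serology negative".

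**The concern.** Diary collection covers every dose and the primary endpoints run to a week after the last one, but the SRC's assessment period is anchored to the first dose only. Cohorts 1 and 2 are the only cohorts given a repeat dose, and they form a dose-escalation pair: 5×10^10 VP, then 1×10^11 VP. Reactions to a repeat dose can differ from those to a first dose, so a clean Day 8 review does not settle the question.

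Two decisions could use the second-dose data: whether Cohort 2's Day 22 dose stays at 1×10^11 VP, if it is still to be given, and whether subcutaneous dosing in Cohorts 3 and 5 stays at that level. The plan already provides the action, which is reduction to 5×10^10 VP. It does not schedule the review that would inform it. One inference of mine adds weight: Cohorts 3 to 6 enrol seropositive participants, and before Cohort 3 the second doses are this trial's only experience of vaccinating people already exposed to the antigen.

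**Working it through.** **1. The plan's own figure.** Day 1 + 7 = Day 8, as stated. The same rule applied to the second dose gives Day 22 + 7 = Day 29, which is the Table 9 visit 7 days after dose 2.

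**2. Triggers set against second doses.**

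| Cohort reviewed | Trigger | What it governs | Second dose | 7 days after second dose |
|---|---|---|---|---|
| 1 | Day 8 | Cohort 2 enrolment | Day 22 | Day 29 |
| 2 | Day 8 | Cohort 3 enrolment | Day 22 | Day 29 |
| 3 | Day 8 | Cohort 4 enrolment | none | none |
| 4 | Day 8 | Cohort 5 enrolment | none | none |
| 5 | Day 8 | Cohort 6 enrolment | none | none |

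For a given participant in Cohorts 1 and 2, the trigger day precedes the second dose by 22 − 8 = 14 days and the end of its 7-day follow-up by 29 − 8 = 21 days. No row has a trigger at Day 22 or Day 29.

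**3. Participants concerned.** Cohorts 1 and 2: 2 × 10 = 20 planned second-dose recipients. Cohorts 3 and 5: 2 × 10 = 20 planned recipients of subcutaneous 1×10^11 VP whose dose the review could inform.

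**4. Could Cohort 1's Day 29 data precede Cohort 2's Day 22 dose?** Cohort 2 cannot start before the last Cohort 1 participant reaches Day 8. At the earliest, its first second dose falls 21 days after that, on that participant's day 8 + 21 = 29. On nominal days the data are therefore due on or before that dose. Table 9 allows ±1 day at each visit. A Cohort 1 second dose one day late, its 7-day visit one day late and a Cohort 2 second dose one day early move the order by 1 + 1 + 1 = 3 days, if the 7-day window runs from the actual dose. A review beforehand is often feasible but not guaranteed, hence a requirement that applies when the data are available.

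**5. What one cohort's review can show.** With 10 participants, the chance of at least one event is 1 − (1 − p)^10: 40% at p = 5%, 65% at 10% and 89% at 20%. With 0 of 10 events, the upper two-sided 95% Clopper-Pearson limit is 1 − 0.025^(1/10) = 30.8%. A Day 29 review would pick up common reactions, not rare ones. The Day 8 gates have the same limit.

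**6. Have Cohorts 1 and 2 already been dosed?** The synopsis describes their enrolment in the past tense, and the inclusion criteria set a serology requirement only for Cohorts 3 to 6, with no seronegative criterion left for Cohorts 1 and 2. Against this, the SRC paragraph still uses the future tense for Cohort 2. The balance favours enrolment being complete; whether Day 29 has passed is not stated.

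**The case against.** The strongest reply is that the SRC is not barred from these data. Its remit is to review safety data, without limit to first doses or to one cohort, and later gates may fall after Day 29 for Cohorts 1 and 2. The trial is open-label, so the site sees reactions as they occur. Second doses have a 30-minute assessment, a call at about 3 days, the Day 29 visit with laboratory tests, and further calls. All of this stands. A reader might infer that the SRC will not see second-dose data, or that repeat dosing is unmonitored; the documents support neither. What they lack is a required review.

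Second, the supplied text is a synopsis and schedule. Its footnotes point to a Table 12 that is not included, so SRC procedures or pausing rules may exist elsewhere. This also stands and limits the finding to the text supplied.

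Third, if Cohorts 1 and 2 are past Day 29, the question of Cohort 2's Day 22 dose is moot. That is likely, and it changes the remedy. It does not remove the value of a documented review before more participants receive 1×10^11 VP subcutaneously.

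Fourth, a review required only when data are available could still leave a Cohort 2 second dose given without one. True. But Cohort 1's data may arrive at the same time as that dose or slightly after, and a mandatory hold could disturb the dosing interval. Leaving any wait to the SRC is proportionate.

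**Conclusion.** The point holds as a missing requirement and should be corrected. Every SRC assessment in the supplied text is triggered 7 days after the first dose, and none is tied to the second dose in Cohorts 1 and 2, although those data are collected and are primary. Up to 20 participants' second-dose data have no required SRC review.

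Two stronger readings should be resisted. One is that Cohort 2's second dose at 1×10^11 VP is about to go ahead unreviewed; the text suggests both cohorts are already enrolled, and the SRC is free to look in any case. The other is to turn the gap into a measure of risk, from the share of dosing visits that are second doses or from modelled lags between cohorts. A share of visits measures no risk, and the documents do not give the enrolment or meeting intervals that such lags would need.

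The conclusion assumes that the full protocol body has no second-dose review. If it has one, a cross-reference in the synopsis is enough. Confidence is medium for that reason.

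**What to change.** In the SRC paragraph of the synopsis (and the matching protocol section):

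1. Keep all Day 8 gates.
2. Define the toxicity assessment period for each dose in Cohorts 1 and 2: to Day 8 after the first dose and to Day 29 after the second.
3. Require SRC review of the Day 29 data from both cohorts. If Cohort 2 second doses are still to be given, Cohort 1's Day 29 data are reviewed before Cohort 2's Day 22 dose whenever they are available.
4. If both cohorts are already past Day 29, replace item 3 with one review of their complete second-dose data at the next SRC meeting, before further subcutaneous dosing at 1×10^11 VP in Cohorts 3 and 5.
5. Provide cumulative second-dose data at every later cohort gate.

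The existing reduction to 5×10^10 VP remains the action available. The cost is one or two extra meetings of the existing committee, on data already being collected, and a possible short delay if the SRC chooses to wait.

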In cohorts 3, 4, 5, and 6 of the study only participants who are SARS-CoV-2 antibody serology positive will be enrolled to evaluate boosting of pre-existing SARS-CoV-2 immune responses and compare the effect of route of administration on the efficacy (and magnitude thereof), reactogenicity and safety of the boosting effect. Our objective is to evaluate this novel vaccine candidate for its potential to boost pre-existing immune responses, where it might well have an important application in future to increase the magnitude and breadth of pre-existing immune responses to SARS-CoV-2 (due to either prior infection or prior vaccination) and provide enhanced, more durable immunity and protection against variants. We will test different routes of administration of the booster – that being subcutaneous, sublingual, subcutaneous plus sublingual, and intranasal. The sublingual administration involves use of the same study product but administered by syringe sublingually. The intranasal also involves the same study product with a delivery device designed for intranasal delivery through atomisation.

Study Objectives	Study Endpoints

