Whole blood, serum and saliva for immunogenicity ^g		X	X		X	X			X		X			X		X

Cohorts 3, 4, 5 and 6

Study Period	Baseline/ Screening	Dose 1 and initial follow up			Extended Follow-up								
Visit code	Screening	01.0	02.0	03.0	04.0	05.0	06.0	07.0	08.0	09.0	10.0	11.0	EOS
Study Day	-14 to 0	1	8	15	22	31	61	91	121	151	181	271	366
Days post dose	-	-	7	14	21	30	60	90	120	150	180	270	365
Visit Type	☺	☺	☺	☎	☎	☺	☎	☺	☎	☎	☺	☺	☺
Visit Windows (days)	-	-	± 1	± 1	± 1	± 5	± 5	± 14	± 14	± 14	± 14	± 14	± 28
Study Procedures													
Informed consent	X												
Assessment of Understanding	X												
Eligibility confirmation	X	X											
Demographics	X												
Medical history	X												
Tuberculosis Screening ^l	X												
HIV Risk Reduction Counselling ^m	X					X		X			X	X	X
COVID-19 history	X	X	X	X	X	X	X	X	X	X	X		X
Confirmation of contraceptive measures	X	X				X							
Symptom enquiry		X	X			X		X			X		X
Physical exam ⁱ : height, weight ^b and vital signs ^c	X	X	X			X		X			X		X

Clinical Trial Protocol: AW_001_ProVIVA-SA-1

Concomitant medications	X	X	X			X		X			X		X
Study product administration													
hAd5-S-Fusion+N- ETSD		X											
Baseline reactogenicity assessment		X											
Assessment of immediate reactogenicity AEs ^j		X											
Subject training on diary card		X											
Diary cards issued		X											
Diary cards received and collected, solicited reactogenicity AEs reconciled			X										
In office unsolicited adverse event collection		X	X			X		X			X		
Telephone check-in 3 days (\pm 2) after vaccine administration		X											
Telephone safety follow up for unsolicited AEs and solicited reactogenicity AEs extending beyond 7 days				X	X		X		X	X			
Specimen Collection & Laboratory Assessments													
Urine or serum for Pregnancy test ^h	X	X				X							
Serum for chemistry panel ^{a,d}	X	X	X			X		X			X		
Whole blood for Haematology ^{a,e}	X	X	X			X		X			X		
Urine for Urinalysis ^{a,f}	X	X	X			X		X			X		
Whole blood/ Serum for HIV test ^k	X							X			X	X	X
Serum for Hepatitis B and C serology	X												

Clinical Trial Protocol: AW_001_ProVIVA-SA-1

Serum for SARS-CoV-2 serology	X												
Biospecimens (e.g., NP swabs) for SARS-CoV-2 PCR	X	X	X			X		X			X	X	X
Whole blood, serum and saliva for immunogenicity ^g		X	X			X		X			X		X

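### The permission for low-dose intranasal steroids also covers Cohort 6, which is vaccinated in the nose and has nasal solicited events; eligibility and analysis should address nasal steroid users there

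*Combined protocol and SAP*

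**What the plan says.** One eligibility list serves the whole trial. Item 17 of the Exclusion Criteria removes candidates with "Chronic use (more than 14 continuous days) of any medications that may be associated with impaired immune responsiveness" and then makes an exception: "The use of low dose topical, ophthalmic, inhaled and intranasal steroid preparations will be permitted". The exception is limited to low-dose products but not by cohort.

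Under Study Design, "Up to 60 healthy participants will be divided into 6 cohorts", and the cohort table gives 10 per cohort. Cohort 6 is the only intranasal cohort. It is dosed once, on Day 1, with vaccine given as "VP into each nostril", and the Rationale describes "a delivery device designed for intranasal delivery through atomisation". Its solicited local events begin with "Nasal congestion and coryza" and continue with epistaxis and nasal pain.

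In the objectives and endpoints table, solicited local reactogenicity is a primary safety endpoint. IgG and neutralising-antibody titres and four-fold seroconversion are primary immunogenicity endpoints. The mucosal endpoint, "Mucosal Immunogenicity as assessed by GMT of IgA antibody levels to SARS CoV-2 S protein, RBD and N protein", is exploratory. Comparing routes across Cohorts 3 to 6 on boosting, reactogenicity and safety is a stated aim.

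The Schedule of Events for Cohorts 3 to 6 records concomitant medications at screening, Day 1 and Day 8, among other visits. It also has a baseline reactogenicity assessment on Day 1, which footnote j extends to symptoms that could overlap with reactogenicity. Statistical Methods plans descriptive summaries by cohort and states no rule for steroid users.

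**The concern.** An exception for local steroids is easy to understand when the vaccine is injected under the skin, because drug and vaccine then go to different places. In Cohort 6 the permitted product and the vaccine are applied to the same surface, and the events solicited there are ones that a nasal complaint could also produce.

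Two things are at stake:

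- **Nasal reactogenicity.** An underlying complaint could add congestion, nosebleed or pain to the count, or the product could suppress congestion that the vaccine would have caused.
- **Immune response.** A drug at the vaccination site could affect the response to a vaccine delivered there. That bears on the primary serum endpoints as well as the exploratory IgA.

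Cohort 6 supplies all the intranasal data for the route comparison, and in a group of 10 each person carries a tenth of every rate.

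**Working it through.** **Inputs from the documents.** Six cohorts of 10 (6 × 10 = 60, which reproduces the stated maximum enrolment); Cohort 6 n = 10; exact Clopper-Pearson intervals for seroconversion and log-scale means for GMTs (Statistical Methods). The plan gives no power or precision figure to reproduce.

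**Assumed inputs, because the documents give none.** Prevalence p of nasal steroid use among eligible volunteers, 1% to 10%; a 2- to 10-fold lower titre in a user, for illustration only; SD of log10 titre, 0.3 to 0.6.

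**1. Weight of one user on a rate.** One person changes a proportion by at most 1/10 = 10 percentage points. Exact 95% intervals, applied here to event rates as well:

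| Events | Rate | 95% CI |
|---|---|---|
| 0/10 | 0% | 0 to 30.8% |
| 1/10 | 10% | 0.3 to 44.5% |
| 3/10 | 30% | 6.7 to 65.2% |

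Ten points is a ceiling. It is reached for a given event only if the user's status on that event differs because of the complaint or the product. The same ceiling applies to the seroconversion rate.

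**2. Weight of one user on a GMT.** If one of 10 titres is f-fold lower, the GMT is multiplied by f^(−1/10):

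- f = 2: 0.933, a fall of 6.7%
- f = 4: 0.871, a fall of 12.9%
- f = 10: 0.794, a fall of 20.6%

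For comparison, the 95% CI of a GMT with n = 10 extends by a factor of 10^(t × SD/√10) either way, with t = 2.262 on 9 df. That is 1.64 for SD 0.3 and 2.69 for SD 0.6.

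**3. Chance of at least one user among 10.** This is 1 − (1 − p)^10:

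- p = 1%: 1 − 0.99^10 = 9.6%
- p = 2%: 18.3%
- p = 5%: 40.1%
- p = 10%: 65.1%

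The chance of two or more users is 0.4%, 1.6%, 8.6% and 26.4% respectively. These are chances of enrolling a user, not of a changed result.

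**4. Effect of setting one user aside.** With n = 9, the interval for no events goes from 0 to 30.8% (0/10) to 0 to 33.6% (0/9). If the three reactors are all non-users, it goes from 6.7 to 65.2% (3/10) to 7.5 to 70.1% (3/9). A display without the user therefore loses little precision.

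**The case against.** The case for leaving the text alone has several parts.

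- **Safeguards already exist.** Overlapping symptoms are recorded before dosing, and medications are recorded on Day 1 and Day 8, so a user could be identified and the results re-tabulated. This stands. It weakens any claim that pre-existing congestion would simply be counted as a reaction. However, no stated analysis uses these records.
- **Other criteria narrow the pool.** Exclusion 1 mentions a history of allergies, exclusion 9 bars any infection, and inclusion 8 requires good general health. This stands in part. The allergy phrase sits inside a criterion on serious adverse reactions, so its reach is unclear, and item 17 expressly foresees intranasal steroid users. The probabilities above are not adjusted for these criteria and would be lower if they are applied broadly.
- **The shift is smaller than the sampling uncertainty.** This is true, as steps 1 and 2 show. But a confidence interval describes sampling error and does not account for events with another cause. In a descriptive cohort of 10, the step from 0/10 to 1/10 is the difference between an event not seen and an event seen.
- **The text supplied is mainly a synopsis and schedule.** A fuller medication section may exist elsewhere, so the absence of a Cohort 6 rule is established only for the text available.

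A reader might go further and infer that the exception defeats item 17 in Cohort 6. It does not: systemic corticosteroids above the stated threshold, immunomodulators and the other named agents remain excluded there. A reader might also infer that a user's mucosal IgA would be suppressed. The documents do not support that. The collection is listed as "Whole blood, serum and saliva for immunogenicity", so the mucosal specimen is saliva rather than nasal fluid, and nothing in the documents shows that a low-dose nasal steroid lowers salivary IgA.

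**Conclusion.** The point holds as a modest one. The plan expressly admits low-dose intranasal steroid users to the one cohort in which that product shares its site with the vaccine and with the solicited local events, and the text available gives no rule for handling them. Nasal event counts could be raised or lowered and the response could be affected; the size and direction are unknown. For one user the bound is 10 percentage points on any Cohort 6 rate. The 10% to 65% chance of having at least one user rests wholly on the assumed 1% to 10% prevalence, and the GMT shifts rest on assumed effects. None of this shows that Cohort 6 results would be misleading. It shows an avoidable ambiguity in a primary safety endpoint, which one clause and one pre-specified display would remove.

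**What to change.** 1. **Eligibility.** In item 17, limit the intranasal-steroid permission to cohorts not dosed in the nose. This concerns entry to Cohort 6 only, and nobody is asked to stop a medicine. Cohort-specific criteria already exist, since inclusion 2 applies only to Cohorts 3 to 6.
2. **Analysis.** State that the Day 1 and Day 8 medication records and the Day 1 baseline-symptom record will be used to identify any nasal-product user in Cohort 6. For any such participant, show the nasal adverse events and the immune results (serum endpoints and salivary IgA) with and without that person.

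**Cost.** One clause and one supplementary display, with no new data collection. The pool for 10 places narrows slightly: even at 10% prevalence, 10/0.9 ≈ 11 otherwise eligible volunteers would fill them. Because cohorts open in sequence and Cohort 6 is last, a user declined there may have no other cohort to join. If the sponsor prefers to keep the permission, the analysis step alone would still make any user's influence visible.
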